#### 4. Randomization Procedures

##### **CTEP Investigator Registration Procedures**

Food and Drug Administration (FDA) regulations and National Cancer Institute (NCI) policy require all investigators participating in any NCI-sponsored clinical trial to register and to renew their registration annually.

Registration requires the submission of:

- a completed **Statement of Investigator Form** (FDA Form 1572) with an original signature
- a current Curriculum Vitae (CV)
- a completed and signed **Supplemental Investigator Data Form** (IDF)
- a completed **Financial Disclosure Form** (FDF) with an original signature

Fillable PDF forms and additional information can be found on the CTEP website at [http://ctep.cancer.gov/investigatorResources/investigator\\_registration.htm](http://ctep.cancer.gov/investigatorResources/investigator_registration.htm). For questions, please contact the **CTEP Investigator Registration Help Desk** by email at [[contact]](mailto:[contact]).

##### **CTEP Associate Registration Procedures / CTEP-IAM Account**

The Cancer Therapy Evaluation Program (CTEP) Identity and Access Management (IAM) application is a web-based application intended for use by both Investigators (i.e., all physicians involved in the conduct of NCI-sponsored clinical trials) and Associates (i.e., all staff involved in the conduct of NCI-sponsored clinical trials).

Associates will use the CTEP-IAM application to register (both initial registration and annual re-registration) with CTEP and to obtain a user account.

Investigators will use the CTEP-IAM application to obtain a user account only. (See CTEP Investigator Registration Procedures above for information on registering with CTEP as an Investigator, which must be completed before a CTEP-IAM account can be requested.)

An active CTEP-IAM user account will be needed to access all CTEP and CTSU (Cancer Trials Support Unit) websites and applications, including the CTSU members' website.

Additional information can be found on the CTEP website at [http://ctep.cancer.gov/branches/pmb/associate\\_registration.htm](http://ctep.cancer.gov/branches/pmb/associate_registration.htm). For questions, please contact the **CTEP Associate Registration Help Desk** by email at [[contact]](mailto:[contact]).

##### **CTSU Registration Procedures**

Rev. 7/15

This study is supported by the NCI Cancer Trials Support Unit (CTSU)

##### **IRB Approval:**

Each investigator or group of investigators at a clinical site must obtain IRB approval for this protocol and submit IRB approval and supporting documentation to the CTSU Regulatory Office before they can be approved to enroll patients. Study centers can check the status of their registration packets by querying the Regulatory Support System (RSS) site registration status page of the CTSU member web site by entering credentials

---

at <https://www.ctsu.org>. For sites under the CIRB initiative, IRB data will automatically load to RSS.

#### Downloading Site Registration Documents:

Site registration forms may be downloaded from the E2211 protocol page located on the CTSU members' website.

- Go to <https://www.ctsu.org> and log in to the members' area using your CTEP-IAM username and password
- Click on the Protocols tab in the upper left of your screen
- Click on the **ECOG-ACRIN** link to expand, then select trial protocol **E2211**
- Click on the Site Registration Documents link

#### Requirements for E2211 site registration:

- CTSU IRB Certification (for sites not participating via the NCI CIRB)
- CTSU IRB/Regulatory Approval Transmittal Sheet (for sites not participating via the NCI CIRB)

### Submitting Regulatory Documents

Submit completed forms along with a copy of your IRB Approval *and Model Informed Consent* to the CTSU Regulatory Office, where they will be entered and tracked in the CTSU RSS.

#### Required Protocol Specific Regulatory Documents

1. CTSU Regulatory Transmittal Form.
2. Copy of IRB Informed Consent Document.

**NOTE:** Any deletion or substantive modification of information concerning risks or alternative procedures contained in the sample informed consent document must be justified in writing by the investigator and approved by the IRB.

3. A. CTSU IRB Certification Form.

Or

- B. Signed HHS OMB No. 0990-0263 (replaces Form 310).

Or

- C. IRB Approval Letter

**NOTE:** The above submissions must include the following details:

- Indicate all sites approved for the protocol under an assurance number.
- OHRP assurance number of reviewing IRB
- Full protocol title and number
- Version Date

- **Type of review (full board vs. expedited)**
- **Date of review.**
- **Signature of IRB official**

### **Checking Your Site's Registration Status:**

Check the status of your site's registration packets by querying the RSS site registration status page of the members' section of the CTSU website. (Note: Sites will not receive formal notification of regulatory approval from the CTSU Regulatory Office.)

- Go to <https://www.ctsu.org> and log in to the members' area using your CTEP-IAM username and password
- Click on the Regulatory tab at the top of your screen
- Click on the Site Registration tab
- Enter your 5-character CTEP Institution Code and click on Go

### **Patient Enrollment**

**Patients must not start protocol treatment prior to randomization.**

Rev. 6/14, 7/15

**Treatment should start within ten working days after randomization.**

Patient randomization can occur only after pre-treatment evaluation is complete, eligibility criteria have been met, and the study site is listed as 'approved' in the CTSU RSS. Patients must have signed and dated all applicable consents and authorization forms.

Patient enrollment will be facilitated using the Oncology Patient Enrollment Network (OPEN). OPEN is a web-based registration system available on a 24/7 basis. To access OPEN, the site user must have an active CTEP-IAM account (check at <<https://eapps-ctep.nci.nih.gov/iam/index.jsp>>) and a 'Registrar' role on either the LPO or participating organization roster.

All site staff will use OPEN to enroll patients to this study. It is integrated with the CTSU Enterprise System for regulatory and roster data and, upon enrollment, initializes the patient in the Rave database. OPEN can be accessed at <https://open.ctsu.org> or from the OPEN tab on the CTSU members' side of the website at <https://www.ctsu.org>.

Prior to accessing OPEN site staff should verify the following:

- All eligibility criteria have been met within the protocol stated timeframes.
- All patients have signed an appropriate consent form and HIPAA authorization form (if applicable).

**NOTE:** The OPEN system will provide the site with a printable confirmation of randomization and treatment information. Please print this confirmation for your records.

Further instructional information is provided on the OPEN tab of the CTSU members' side of the CTSU website at <https://www.ctsu.org> or at <https://open.ctsu.org>. For any additional questions contact the CTSU Help Desk at [name] or [[contact]](mailto:[contact]).

The following information will be requested:

#### **4.1 Protocol Number**

4.2 Investigator Identification

- 4.2.1 Institution and affiliate name (Institution CTEP ID)
- 4.2.2 Investigator's name (NCI number)
- 4.2.3 Cooperative Group Credit
- 4.2.4 Credit Investigator
- 4.2.5 Protocol specific contact information

4.3 Patient Identification

- 4.3.1 Patient's initials (first and last)
- 4.3.2 Patient's Hospital ID and/or Social Security number
- 4.3.3 Patient demographics
  - 4.3.3.1 Gender
  - 4.3.3.2 Birth date
  - 4.3.3.3 Race
  - 4.3.3.4 Ethnicity
  - 4.3.3.5 Nine-digit ZIP code
  - 4.3.3.6 Method of payment
  - 4.3.3.7 Country of residence

4.4 Eligibility Verification

Patients must meet all of the eligibility requirements listed in Section [3](#).

4.5 Stratification Factors

Patients will be stratified according to the following factors for purposes of balancing arms:

- 4.5.1 Prior everolimus: Yes v. No
- 4.5.2 Prior sunitinib: Yes v. No
- 4.5.3 Concurrent octreotide: Yes v. No

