#### 3.1 Eligibility Criteria

- \_\_\_\_\_ 3.1.1 Patient must have histologically or pathologically confirmed locally unresectable or metastatic low or intermediate grade pancreatic neuroendocrine tumor, excluding small cell carcinoma.
- \_\_\_\_\_ 3.1.2 Patient must have measurable disease by RECIST 1.1 criteria as defined in Section [6.1.2](#). Baseline measurements and evaluations of all sites of disease must be obtained  $\leq$  4 weeks prior to randomization and must be acquired by multiphasic CT or contrast MRI.
- \_\_\_\_\_ 3.1.3 Patient must have documented disease progression, and date of last documented disease progression must be within 12 months from date of randomization.
- \_\_\_\_\_ 3.1.4 Patient must not have received prior temozolomide, DTIC, capecitabine, or 5-FU therapy.
- \_\_\_\_\_ 3.1.5 Prior everolimus and/or sunitinib therapy is allowed, so long as it was discontinued  $\geq$  4 weeks prior to randomization.
- \_\_\_\_\_ 3.1.6 Concurrent somatostatin analogues are allowed provided that the patient 1) has been on a stable dose (+/- 10mg) for 8 weeks and 2) has documented disease progression on that dose.
- \_\_\_\_\_ 3.1.7 Chemoembolization is allowed if  $\geq$  4 weeks from study entry. There are 3 possible scenarios:
  - \_\_\_\_\_ 3.1.7.1 If patient has hepatic disease only: they need to have progressed in the liver since chemoembolization and have measurable disease by RECIST 1.1 in order to be eligible.
  - \_\_\_\_\_ 3.1.7.2 If patient has hepatic and extrahepatic disease: they will need to have progressed inside OR outside the liver and

have measurable disease by RECIST 1.1 in order to be eligible.

- 3.1.8 Patients may not be receiving any other investigational agents while on study treatment.
- 3.1.9 Patients may not be receiving Coumadin while on treatment. Other anticoagulants are allowed.
- 3.1.10 Patients must have normal organ and marrow function as defined below within  $\leq$  14 days prior to randomization:
  - 3.1.10.1 Leukocytes  $\geq$  3,000/mm^3  
Leukocytes \_\_\_\_\_ Date: \_\_\_\_\_
  - 3.1.10.2 Absolute neutrophil count  $\geq$  1,500/mm^3  
Neutrophil count: \_\_\_\_\_ Date: \_\_\_\_\_
  - 3.1.10.3 Hemoglobin  $\geq$  9 g/dL  
Hemoglobin: \_\_\_\_\_ Date: \_\_\_\_\_
  - 3.1.10.4 Platelets  $\geq$  100,000/mm^3  
Platelets: \_\_\_\_\_ Date: \_\_\_\_\_

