  - 3.1.10.5 Total bilirubin  $\leq$  institutional upper limit of normal (ULN) or  $\leq$  1.5 X institutional ULN (if the patient has liver metastases).  
ULN: \_\_\_\_\_ Bilirubin: \_\_\_\_\_ Date: \_\_\_\_\_
  - 3.1.10.6 AST(SGOT)/ALT(SGPT)  $\leq$  3 X institutional ULN or ( $\leq$  5 X institutional ULN if the patient has liver metastases).  
ULN: \_\_\_\_\_ AST \_\_\_\_\_ Date: \_\_\_\_\_  
ULN: \_\_\_\_\_ ALT \_\_\_\_\_ Date: \_\_\_\_\_
  - 3.1.10.7 Serum Creatinine  $\leq$  1.5 X institutional ULN  
ULN: \_\_\_\_\_ Creatinine: \_\_\_\_\_ Date: \_\_\_\_\_
- 3.1.11 Patient must be at least 18 years of age.
- 3.1.12 Patient must have ECOG performance status 0-1.
- 3.1.13 Patient must have life expectancy  $\geq$  12 weeks.
- 3.1.14 Patients with either clinically apparent central nervous system metastases or carcinomatous meningitis are ineligible.
- 3.1.15 Patients must NOT have active or uncontrolled infection or serious medical or psychiatric illness.
- 3.1.16 Patients must NOT have history of allergic reactions attributed to compounds of similar chemical or biologic composition to temozolomide or capecitabine.

\_\_\_\_\_ 3.1.17 Patient must NOT have absorption issues that would limit the ability to absorb study agents.

\_\_\_\_\_ 3.1.18 Patients with a history of the following within  $\leq$  12 months of study entry are not eligible.

- Arterial thromboembolic events: Yes \_\_\_\_\_ Date: \_\_\_\_\_ No: \_\_\_\_\_
- Unstable angina: Yes \_\_\_\_\_ Date: \_\_\_\_\_ No: \_\_\_\_\_
- Myocardial Infarction: Yes \_\_\_\_\_ Date: \_\_\_\_\_ No: \_\_\_\_\_

\_\_\_\_\_ 3.1.19 Patients with symptomatic peripheral vascular disease are not eligible.

\_\_\_\_\_ 3.1.20 Patients must NOT have previous or concurrent malignancy. Exceptions are made for patients who meet any of the following conditions:

- Non-melanoma skin cancer, in situ cervical cancer, or breast cancer in situ.

OR

- Prior malignancy completely excised or removed and patient has been continuously disease free for  $>$  5 years.

OR

- Prior malignancy cured by non-surgical modalities and patient has been continuously disease free for  $>$  5 years.

Date of last evidence disease: \_\_\_\_\_

\_\_\_\_\_ 3.1.21 Women must not be pregnant or breast-feeding due to potential harm to fetus from temozolomide and/or capecitabine.

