### 9.2 Treatment Assignment

Patients will be randomized with equal probability to treatment with single agent temozolamide or the combination of temozolamide and capecitabine using a stratified permuted blocks algorithm with stratification based on prior treatment with everolimus (Yes vs No), prior treatment with sunitinib (Yes vs No) and concurrent administration of octreotide (Yes vs No).

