### 9.3 Statistical Design and Efficacy Monitoring

The primary endpoint of this trial is progression-free survival (PFS). Patient assessments will be made every 3 months.

This study will require a minimum of 138 patients (or a maximum of 145 patients to allow for 5% ineligibility) to be accrued at the rate of roughly 6 patients per month. With 23 months of accrual time and 13 months of follow-up (3 years total study time), this trial will have at least 81% power to detect a difference in median PFS between the treatment arms of 9 versus 14 months (hazard ratio of 0.64) using a two-sided log-rank test at the overall 0.20 significance level. The assumption of 9 months for the temozolamide arm is based on historical data of temozolamide alone and temozolamide-based regimens as described in the introduction. The assumption of 14 months for the combination arm is based a goal of improving treatment by 55% (which conservatively approximates the Strosberg PFS data of 18 months).

There will be two log-rank tests conducted, an interim analysis at 76% information (at 80 PFS events, projected to occur just after the end of the accrual period at 26 months) and a final analysis at 100% information (105 PFS events), projected to occur at 3 years from the start of accrual. The overall type I error will be controlled using an O'Brien-Fleming boundary function. Using this boundary, if the repeated two-sided 95% confidence interval on the hazard ratio does not contain the target alternative hazard ratio of 0.64, consideration will be given to declaring the study negative and reporting the results. If the interim log-rank test is positive, the study can be reported early before the projected end of the follow-up period.

Response rate (RR) will be a secondary endpoint. RR will be defined by revised RECIST criteria version 1.1 and include complete responses and partial responses. Prior studies of single agent temozolomide suggest that the response rate associated with single-agent temozolomide is 8-24%; however, overall response rates associated with other temozolomide-based regimens in this disease are between 30-40%. For the purposes of this study, we assume that single agent temozolomide will be associated with a response rate of 33%. Retrospective series of temozolomide/capecitabine have reported response rates of 59-70% in advanced pancreatic neuroendocrine tumors.

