### 12.1 Pathology Review

The appropriate representative tumor tissue samples will be forwarded to [name] for central diagnostic review and classification to confirm the diagnosis of low or intermediate grade pNET. This is a retrospective review to determine the evaluability of the patient's data for data analysis. The results of the review are for the purpose of the trial only and will not be returned to the site.

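### The PFS comparison uses no baseline covariate, and neither ECOG performance status nor tumour grade is balanced or adjusted for: the test is valid, but efficiency and protection against chance imbalance are left to luck

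*Combined protocol and SAP*

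**What the plan says.** **Randomisation.** Section 4.5 reads "Patients will be stratified according to the following factors for purposes of balancing arms". The three factors are prior everolimus, prior sunitinib and concurrent octreotide, and Section 9.2 repeats them for the permuted blocks. All three are treatment history or concurrent therapy. None is a disease or patient feature.

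**Population.** Criterion 3.1.1 admits "locally unresectable or metastatic low or intermediate grade pancreatic neuroendocrine tumor, excluding small cell carcinoma", and 3.1.12 reads "Patient must have ECOG performance status 0-1". The Section 7.1 calendar has PS assessed before randomisation. Grade appears in the checklist as one combined item. The registration items in Sections 4.2 to 4.5 do not ask for low versus intermediate. The local pathology report must be sent in for every patient (Section 11.1.1, Appendix I). Section 12.1 adds a central review "to confirm the diagnosis of low or intermediate grade pNET", described as follows: "This is a retrospective review to determine the evaluability of the patient's data for data analysis".

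**Analysis.** Section 9.3 bases power on comparing PFS "using a two-sided log-rank test at the overall 0.20 significance level", with an interim look at 80 events, a final look at 105 and an O'Brien-Fleming boundary. A repeated confidence interval for the hazard ratio (HR), checked against 0.64, may lead to the study being declared negative. No strata, covariates or adjusted PFS model are named, and even the three randomisation factors are not said to enter the comparison.

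**The concern.** If a covariate predicts PFS, leaving it out of a time-to-event comparison pulls the HR toward 1 and costs some power. With 69 patients per arm and no balancing on the covariate, a chance difference between arms also moves the estimate. That estimate feeds the interim rule comparing the interval with 0.64. If an imbalance in grade or PS appears once PFS results are known, any adjustment made then is post hoc and open to challenge. Analysing by the three randomisation factors would not meet the point, because they are different covariates.

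**Working it through.** **1. The plan's own power.** Inputs from Section 9.3: 105 events, medians 9 and 14 months (HR 9/14 = 0.643), two-sided 0.20 (z = 1.2816), 1:1 allocation.

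- Schoenfeld, fixed design: (√105 / 2) × |ln 0.643| − 1.2816 = 5.123 × 0.4418 − 1.2816 = 0.982, so power is 83.7%. Freedman's formula gives 82.8%.
- With one O'Brien-Fleming look at 80/105 information: 82.7% to 82.8%.
- Expected events at 36 months, with exponential PFS and uniform accrual over 23 months: P(event) = 1 − (e^(−13λ) − e^(−36λ)) / (23λ), which is 0.828 for λ = ln 2/9 and 0.686 for λ = ln 2/14. Then 69 × (0.828 + 0.686) = 104.5, against the stated 105.

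The stated figure of at least 81% reproduces. These formulas assume a common hazard within each arm.

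**2. Chance imbalance.** Treat the number with the feature in each arm as Binomial(69, p), independent of the randomisation strata. A difference of 10 points or more means at least 7 patients.

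| Assumed prevalence p | P(10 points or more) | P(15 points or more) |
|---|---|---|
| 0.3 | 22.7% | 5.1% |
| 0.4 | 25.9% | 6.8% |
| 0.5 | 26.8% | 7.3% |

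These are two-sided and per factor; about half of each is against the combination arm. A 10-point imbalance multiplies the unadjusted HR by about exp(0.10 × ln h). For a prognostic HR h of 1.5 this is 1.041 (0.643 becomes 0.669). For h of 2.0 it is 1.072 (0.643 becomes 0.689).

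**3. Power with and without adjustment.** The documents give neither a prognostic effect nor a split for grade or PS, so these are assumed: 50% intermediate grade, 40% PS 1, prognostic HRs 1.0 to 2.0. The simulation used 138 patients, 23 months' accrual, a cut at 105 events, overall arm medians of 9 and 14 months, two-sided 0.20 and no interim look. Two runs of 5,000 trials per setting were made (Monte Carlo error about 0.5 point each). The Cox model held treatment, grade and PS.

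| Prognostic HR (grade, PS) | Log-rank, runs 1 / 2 | Cox, runs 1 / 2 | Mean change |
|---|---|---|---|
| 1.0, 1.0 | 84.2 / 83.1% | 83.4 / 82.5% | −0.7 |
| 1.5, 1.3 | 81.9 / 80.9% | 83.1 / 82.3% | +1.3 |
| 1.5, 1.5 | 80.2 / 81.7% | 82.4 / 83.2% | +1.9 |
| 2.0, 1.5 | 78.1 / 78.7% | 82.7 / 83.2% | +4.6 |
| 2.0, 2.0 | 76.3 / 76.6% | 82.6 / 84.1% | +6.9 |

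A further independent simulation gave 83.6% vs 83.4% with no prognostic effect, 80.1% vs 81.9% at 1.5/1.5 and 76.5% vs 82.5% at 2.0/2.0.

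In run 2, the combination arm had at least 10 points more intermediate grade in about 13% of trials. For grade HRs of 1.5 to 2.0, power in those trials was 63-74% unadjusted and 82-85% adjusted.

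**4. Type I error.** With no treatment effect and prognostic HRs 2.0 and 1.5, rejection in favour of the combination was 10.5% (log-rank) and 10.8% (Cox), against a nominal 10%. The further simulation gave two-sided rejection of 19.9% and 19.7% against 20%.

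**5. Stratifying instead.** A log-rank test stratified by grade × PS cost about 2 points when neither factor was prognostic (84.2% to 82.1%; 83.1% to 81.3%). It roughly broke even near HR 1.5 and gained about 3 to 6 points at the strong end. Adding both factors to the permuted blocks would raise the cells from 2³ = 8 to 2⁵ = 32, or 138/32 = 4.3 to 145/32 = 4.5 patients per cell.

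**Limits.** The simulations include no interim look, no misclassification of local grade (which would shrink the gain) and not the three randomisation factors.

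**The case against.** Nothing in the documents says that grade or PS predicts PFS here, how strongly, or in what proportions patients will fall. At prognostic HRs near 1 adjustment gains nothing, and at 1.5 the gain is 1 to 2 points. Chance imbalance is ordinary sampling variation that a valid test and its interval already reflect, and it can favour either arm. An unadjusted log-rank test is a defensible primary test for a randomised phase II trial at two-sided 0.20, and three stratification factors already make eight cells.

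This stands as far as it goes: there is no error in the test, and the size is conditional. It does not answer the absence of any prespecified adjusted estimate, when having one costs almost nothing.

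A reader might also infer that both factors are known at entry as ready-made covariates. That is firm for PS only. Low versus intermediate grade is a single checklist item, and central review comes after randomisation and depends on tissue being submitted. The data forms are not part of the documents, so whether grade is captured separately cannot be told from them.

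Two points bear on the remedy. Reporting an adjusted HR beside the log-rank test recovers none of the test's power. Changing only the final test would leave the interim look and boundary on a different statistic.

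**Conclusion.** The point holds as one of efficiency and chance imbalance, not validity. PS and grade are neither balanced nor adjusted for, and no PFS analysis in Section 9.3 would correct an imbalance in them.

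Under the assumed prevalences and prognostic HRs of 1.0 to 2.0, Cox adjustment changes power by about -1 to +7 points. The unadjusted test falls below 81% only towards the stronger end of that range. An imbalance of 10 points or more in any one factor has about 23-27% probability at prevalences of 30% to 50%.

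A reader might conclude that power is definitely being lost or that the 81% is wrong. The documents do not support either: the figure reproduces for the design as written, and any loss requires a prognostic effect that they do not state. Nor is there a type I error problem.

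**What to change.** In Section 9.3, before any PFS comparison, prespecify a Cox model for PFS with treatment, ECOG PS (0 vs 1), the three randomisation factors and locally reported grade (low vs intermediate, abstracted from the pathology report already required). Report its HR and interval as the prespecified adjusted estimate beside the log-rank test. This leaves the test, alpha and boundary unchanged. It protects interpretation against chance imbalance but does not raise the power of the test.

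If the adjusted model is instead to be the test, use it at both the 80-event and 105-event looks, with the same O'Brien-Fleming boundary and the same repeated confidence interval rule, so that interim and final rest on one statistic.

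Cost: a short addition to Section 9.3 and, for grade, one form item. The HR becomes conditional on the covariates, and the text should say so. If grade is not captured, adjust for PS and the randomisation factors only. Randomisation and sample size do not change.
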